10.3. Statistical Analyses

10.3.1. General Statistical Considerations

Statistical analysis of this study will be the responsibility of Lilly or its designee. A detailed SAP describing the statistical methodologies will be developed by Lilly or its designee.

Any change to the data analysis methods described in the protocol will require an amendment ONLY if it changes a principal feature of the protocol. Any other change to the data analysis methods described in the protocol, and the justification for making the change, will be described in the clinical study report (CSR). Additional exploratory analyses of the data will be conducted as deemed appropriate.

All tests of treatment effects will be conducted at a 2-sided alpha level of 0.05, unless otherwise stated (e.g., refer to Section 10.3.7.3). Treatment comparisons of discrete efficacy variables between baricitinib and placebo will be made using a logistic regression analysis with region, disease severity, age, treatment group, and treatment group-by-age interaction in the model. The percentages, difference in percentages, and 95% confidence interval (CI) of the difference in percentages will be reported. Treatment-by-age interaction will be added to the logistic regression model of the primary and key secondary variables as a sensitivity analysis. If this interaction is significant at a 2-sided 0.1 level, further inspection will be used to assess whether the interaction is quantitative (i.e., the treatment effect is consistent in direction but not size of effect) or qualitative (the treatment is beneficial for some but not all age groups). The p-value from the Fisher exact test will also be produced.

When evaluating continuous measures over time, a restricted maximum likelihood-based mixed-effects model of repeated measures (MMRM) will be used. The model will include treatment, age cohort, baseline severity, visit, and treatment-by-visit interaction, and treatment-by-age cohort interaction as fixed categorical effects and baseline score and baseline score-by-visit interaction as fixed continuous effects. Region may be included in the model if

applicable. An unstructured (co)variance structure will be used to model the between- and within-patient errors. If this analysis fails to converge, other structures will be tested. The Kenward–Roger method will be used to estimate the degrees of freedom. Type III sums of squares for the least squares means (LSMs) will be used for the statistical comparison; 95% CI will also be reported. Contrasts will be set up within the model to test treatment groups at specific time points of interest. Further details on the use of MMRM will be described in the SAP.

Treatment comparisons of continuous efficacy and health outcome variables may also be made using analysis of covariance (ANCOVA) with region, disease severity, treatment group, and baseline value in the model. Type III tests for LSM will be used for statistical comparison between treatment groups. The LSM difference, standard error, p-value, and 95% CI may also be reported. The method used to handle missing data will be specified in the SAP.

Fisher’s exact test will be used for the AEs, discontinuation, and other categorical safety data for between-treatment group comparisons. Continuous vital signs, body weight, and other continuous safety variables including laboratory variables will be analyzed by an ANCOVA with treatment and baseline value in the model. Shift tables for categorical safety analyses (e.g., “high” or “low” laboratory results) will also be produced.

Missing data imputation:

1. Nonresponder imputation (NRI): All patients who discontinue the study or the study treatment at any time for any reason will be defined as nonresponders for the NRI analysis for categorical variables such as IGA 0/1 or EASI 50/75/90 after discontinuation and onward. Patients who receive rescue therapy will be analyzed as nonresponders after rescue and onward. An additional analysis will be performed that includes all available data whether rescue medication was given or not.
2. Continuous variables such as EASI and SCORAD scores will be assumed to be missing after rescue or discontinuation and then an MMRM analysis will be performed. An additional analysis will be performed that includes all available data whether rescue medication was given or not.
3. Last observed carried forward (LOCF). An additional analysis will be performed that uses the last observed value on or prior to discontinuation or rescue therapy. This will then be analyzed using a logistic model for categorical variables or ANCOVA for continuous variables as described above.

Additional sensitivity analyses for the primary and key secondary endpoints such as a reference based multiple imputation method may be performed and will be specified in the SAP.

Adjustment for Multiple Comparisons:

Multiplicity controlled analyses will be performed on the primary and major secondary endpoints to control the overall family-wise Type I error rate at a 2-sided α level of 0.05. The graphical multiple testing procedure described in Bretz et al. (2011) will be used. The graphical approach

is a closed testing procedure; hence it strongly controls the family-wise error rate across all endpoints (Alosh et al. 2014). Each dose of baricitinib will be tested separately using the graphical approach. Details of the specific graphical testing scheme (including testing for each dose of baricitinib and testing order, interrelationships, Type I error allocation, and the associated propagation) will be prespecified in the SAP.

The following is a list of primary and key secondary endpoints to be tested:

Primary:

- proportion of baricitinib-treated patients (at each dose) achieving IGA of 0 or 1 and ≥ 2 -point improvement from baseline at Week 16.

Key Secondaries Evaluated for Each Baricitinib Dose (high, medium, and low):

- proportion of patients achieving EASI75 at 16 weeks
- proportion of patients achieving EASI90 at 16 weeks
- mean change from baseline in EASI score at 16 weeks
- proportion of patients achieving SCORAD75 at 16 weeks
- proportions of patients achieving a 4-point improvement in Itch NRS at 1 week, 2 weeks, 4 weeks, and 16 weeks

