Approximately 440 patients will be enrolled into the Double-blind Treatment period (with at least 320 patients aged 10 to <18 years old and at least 120 patients aged 2 to <10 years old).

Statistical Analysis:

Approximately 25 patients will be enrolled into the Open-label PK Lead-in (Study Period 2) and may continue on open-label treatment during the long-term extension (Study Period 4). Data from patients participating in the PK lead-in will be analyzed separately from patients randomized into the Double-blind Treatment (Study Period 3).

Approximately 440 patients 2 to <18 years of age will participate in the Double-blind Treatment period (Study Period 3) and will be randomized at a 1:1:1:1 ratio to receive placebo QD, baricitinib low dose QD, baricitinib medium dose QD, or baricitinib high dose QD (110 patients in each treatment group). Patients will be stratified at randomization according to disease severity (Investigator's Global Assessment [IGA] 3 vs. 4) and geographic region if the planned country allocation justifies.

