7.2. Method of Treatment Assignment

Patients participating in the PK lead-in who meet all criteria for enrollment will receive open label baricitinib at the high dose for their age group beginning at Visit 2.

Patients not participating in the PK lead-in who meet all criteria for enrollment will be randomized in a 1:1:1:1 ratio (placebo, baricitinib low dose; baricitinib medium dose; baricitinib high dose) to double-blind treatment at Visit 2. Assignment to treatment groups will be determined by a computer-generated random sequence using an interactive web-response system (IWRS). The IWRS will be used to assign blister packs or bottles containing double-blind IP to each patient according to the Study Schedule (Section 2). Site personnel will confirm that they have located the correct blister packs or bottles by entering a confirmation number found on the blister packs or bottles into the IWRS.

Randomization will be stratified by disease severity at baseline (IGA 3 versus 4) and geographic region if the planned country allocation justifies. Definitions of geographic regions and plan for analysis by region will be described in the SAP.

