10.1. Sample Size Determination

Approximately 25 patients will be enrolled into the Open-label PK Lead-in (Study Period 2) and may continue on open-label treatment during the long-term extension (Study Period 4). Data from patients participating in the PK lead-in will be analyzed separately from patients randomized into the Double-blind treatment (Study Period 3).

Study JAIP will aim to enroll at least 440 patients 2 to <18 years of age into the Double-blind Treatment period (Study Period 3), which includes at least 320 older pediatric patients (10 to <18 years) and at least 120 younger pediatric patients (2 to <10 years). The proposed sample size (N=440) will ensure a >95% power to detect any difference between the baricitinib high dose and placebo treatment groups or the baricitinib medium dose and placebo treatment groups, each using a 2-sided alpha of 0.05, assuming a 10% placebo, 25% medium dose, and 30% high dose response rate for the primary endpoint using a chi-squared test. The assumptions are based on what was observed in the Phase 2 study (JAHG). The proposed end point of IGA 0 or 1 represents patients whose AD is clear or almost clear from a baseline of moderate or severe disease. The anticipated effect size represents 3 times more patients achieving this benefit compared to placebo which, in discussion with therapeutic experts, is of a magnitude that is considered to be clinically relevant.

Furthermore, in older pediatric patients the sample size of 320 is sufficient to detect that the baricitinib high or medium dose is superior to placebo at least 80% of the time. Similarly, in the younger pediatric patients, the planned sample size of 120 patients has > 80% simulated power using the Bayesian approach described in Section 10.3.7.3 and in the Study JAIP SAP to detect any difference between the baricitinib high dose or medium dose and placebo treatment groups with a probability threshold of 0.95.

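### Section 10.3.1's main MMRM pairs a treatment-by-age cohort term with Type III least squares means, so by convention 27% of patients carry half of the Week 16 EASI estimate, at up to about 26% more variance

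*Protocol*

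**What the plan says.** Section 10.3.1 of the protocol defines the repeated-measures model for continuous measures. Its fixed effects include treatment-by-visit and "treatment-by-age cohort interaction as fixed categorical effects". There is no treatment-by-age-by-visit term. For inference, "Type III sums of squares for the least squares means (LSMs) will be used for the statistical comparison", and "Contrasts will be set up within the model to test treatment groups at specific time points of interest". The section does not say how the least squares means or contrasts weight the two age cohorts. It closes with "Further details on the use of MMRM will be described in the SAP".

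Section 10.1 plans "at least 320 older pediatric patients (10 to <18 years) and at least 120 younger pediatric patients (2 to <10 years"), and Section 5.1 gives "110 patients in each treatment group". Age is not a randomisation factor. Section 7.2 says "Randomization will be stratified by disease severity at baseline (IGA 3 versus 4) and geographic region if the planned country allocation justifies".

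Mean change in EASI at Week 16 is among the multiplicity-controlled key secondary endpoints in Section 10.3.1. Section 10.3.3.2 assigns the same MMRM to SCORAD, BSA, POEM, DFI and other continuous measures. Section 10.3.7.3 separately plans an MMRM for EASI with an added subgroup variable and a subgroup-by-treatment interaction, and lists age (under 10, or 10 and over) as one of the subgroups.

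**The concern.** With an interaction in the model, a Type III treatment comparison is ordinarily the comparison of unweighted marginal means. Each cohort's treatment effect gets weight one half, whatever its size. Two things follow.

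- **The target changes.** If the effect differs by age, the reported difference describes a population that is half under 10, although only about 27% of the planned sample is.
- **Precision is lost.** The smaller cohort is noisier and is weighted up.

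The protocol gives no reason for either. Section 10.2 sets all randomised patients as the efficacy population. The alternative ANCOVA in Section 10.3.1 has no age term, so the two analyses of one endpoint would target different age mixes. The age interaction already has a place in Section 10.3.7.3.

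**Working it through.** **Stated figures.** The protocol gives no SD, effect size or power for EASI change. Its power of more than 95% (Section 10.1) concerns the primary endpoint. With 110 per arm, 10% versus 30% and two-sided 0.05 it reproduces for the high dose (96.4%). It does not bear on this point.

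**Inputs.** 320 older and 120 younger patients, 1:1:1:1, so about 80 and 30 per arm (Sections 10.1 and 5.1). Two-sided alpha is 0.05 (Section 10.3.1). Six post-baseline visits run from Week 1 to Week 16 (Table JAIP.2). Assumed: two cohorts, equal residual variance s² in both, complete data.

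**Shift in target.** Population weights are 320/440 = 0.727 and 120/440 = 0.273. Equal weights are 0.5 and 0.5. As an invented illustration, take effects of -5 (older) and -2 (younger) EASI points:
- population-weighted: 0.727 × (-5) + 0.273 × (-2) = -4.2
- equally weighted: (-5 - 2)/2 = -3.5

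This shift does not depend on the covariance.

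**Variance at a single visit.**
- equal weights: ¼(2s²/80 + 2s²/30) = 0.02292 s²
- cohort-size weights: 2s²/110 = 0.01818 s²
- ratio 1.260; the standard error is 12.3% larger; effective size is about 87 per arm instead of 110

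**Variance in the model as written.** Without a three-way term, the cohort difference within an arm is constant over visits and is estimated from all six. With V the within-patient covariance matrix over visits and 1 a vector of ones, the per-arm variance of the equally weighted Week 16 mean is

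s²/110 + (0.5 - 30/110)² × (1/80 + 1/30) / (1'V⁻¹1).

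Dividing by s²/110, where (0.2273)² × 0.04583 × 110 = 0.260, gives

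ratio = 1 + 0.260 / (s² × 1'V⁻¹1).

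The quantity s² × 1'V⁻¹1 is at least 1, because pooling visits cannot do worse than using Week 16 alone. So 1.260 is a ceiling. It is reached if the other visits add nothing, or if a three-way term is fitted. Under compound symmetry s² × 1'V⁻¹1 = 6/(1 + 5ρ). At ρ = 0.5 that is 1.714, and 0.260/1.714 = 0.15.

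| Assumed covariance | ρ = 0.3 | 0.5 | 0.7 | 0.9 |
|---|---|---|---|---|
| Compound symmetry | +11% | +15% | +20% | +24% |
| AR(1) | +7% | +10% | +14% | +21% |
| Compound symmetry, SD rising over visits (0.6 to 1.0 of the Week 16 SD) | +6% | +8% | +8% | +5% |

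**Effect on power.** For 90% power under population weights, the standardised effect is 1.960 + 1.282 = 3.242.
- +5%: 3.242/√1.05 - 1.960 = 1.20, power about 89%
- +24%: 3.242/√1.24 - 1.960 = 0.95, power about 83%
- ceiling: 82.3%

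Starting from 80%, the same steps give about 78% and 71%, with 70.4% at the ceiling.

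**The case against.** The strongest reply is that the protocol never states equal weights. It leaves the contrast coefficients open and defers MMRM details to the SAP, which was not available here. Observed-margin means or weighted contrasts would fit the same text. This stands in part: equal weighting is inferred from the usual meaning of the named method. But the protocol itself fixes both the interaction term and the Type III basis, and a programmer following it as written would obtain the 50:50 estimate.

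A second reply is that 73:27 is not the only defensible target. The cohort sizes are minimums, the cohorts differ in dose and formulation, and age-specific effects are a declared interest. That is fair, but Section 10.3.1 does not declare a 50:50 target either, and Section 10.3.7.3 already serves the age-specific question. If the older cohort finishes more than 6 months ahead, Section 10.3.8 makes the combined analysis secondary, and the point then matters less.

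A reader might also infer more than the documents support:

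- **A 26% variance increase in this MMRM.** That is the single-visit figure. No covariance tried for the written model reached it.
- **Every continuous endpoint is affected.** The two TCS-use measures use an ANCOVA with treatment and baseline only (Section 10.3.3.2). Measures confined to one cohort, such as Itch NRS and PRISM, are outside it too.
- **A stated power figure or the type I error rate is compromised.** No power is stated for EASI change, and equal weighting does not inflate type I error when neither cohort has a treatment effect.

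**Conclusion.** The point holds as a matter of estimand and efficiency. Read conventionally, the main MMRM gives about 27% of patients half the weight for Week 16 EASI change and for the other MMRM endpoints collected in both cohorts. The variance cost is bounded at about 26%. For the model as written it is about 5% to 24% over the covariances tried. The change of target population is the firmer part, because it needs no covariance assumption; it matters only if the treatment effect differs by age.

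The sizes rest on two cohorts, equal variance, complete data and a split of about 80/30 per arm, which randomisation does not enforce because age is not a stratification factor. The correction should be made, but the trial's stated claims do not depend on it. If the SAP already sets cohort-size weights, the point is closed.

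**What to change.** In Section 10.3.1, do one of the following:

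1. Remove treatment-by-age cohort from the main MMRM, keep age cohort as a main effect, and assess the interaction in the age-subgroup MMRM already planned in Section 10.3.7.3.
2. Keep the term and state that least squares means and contrasts use observed-margin weights, that is, the age-cohort proportions of the randomised population.

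Either choice returns the variance to about 2s²/110 and points the estimate at the enrolled age mix. The cost is one sentence in the protocol or SAP and the matching program option, with no patients or data. If equal weighting is intended, the protocol should say so and give the reason.

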10.3.2. Treatment Group Comparability

10.3.2.1. Patient Disposition

All patients who discontinue from the study or the study treatment will be identified, along with their reason for discontinuation. Reasons for discontinuation from the study will be summarized by treatment group.

10.3.2.2. Patient Characteristics

Demographic and baseline characteristics will be summarized descriptively by treatment group. Descriptive statistics including number of patients, mean, standard deviation, median, minimum, and maximum will be provided for continuous measures, and frequency counts and percentages will be tabulated for categorical measures. No formal statistical comparisons will be made among treatment groups unless otherwise stated.

10.3.2.3. Concomitant Therapy

Concomitant medications will be descriptively summarized by treatment group in terms of frequencies and percentages using the safety population. The medications will be coded accordingly.

10.3.2.4. Treatment Compliance

Treatment compliance will be evaluated at every clinic visit. A patient will be considered significantly noncompliant if he or she misses more than 20% of the prescribed doses during the study, unless the patient's IP is withheld by the investigator for safety reasons; that is, compliance $< 80\%$. Similarly, a patient will be considered significantly noncompliant if he or she

is judged by the investigator to have intentionally or repeatedly taken more than the prescribed amount of medication, that is, compliance $\geq 120\%$.

10.3.3. Efficacy Analyses

10.3.3.1. Primary Analyses

The primary efficacy measure is the binary outcome of response defined as IGA score of 0 or 1 (clear or almost clear skin) and ≥ 2 -point improvement from baseline at Week 16. The primary analysis will be conducted using a logistic regression analysis with region, disease severity (IGA), age, treatment group, and treatment group-by-age interaction in the model. Nonresponder imputation for missing data as described above will be used.

The primary analysis will include data from the entire study population 2 to <18 years old and will use a frequentist analysis approach. However, in the event that the older subgroup of patients (10 to <18 years old) completes the Double-blind Treatment period (Study Period 3) more than 6 months earlier than the anticipated completion for the younger subgroup of patients (2 to <10 years old), each age subgroup will be unblinded and analyzed separately according to a pre-planned analysis approach as described in Section 10.3.8 below. This is to ensure that potential delay in completing the enrollment of the younger patients will not delay analysis and submission of the data from the older patients.

Additional analysis of the primary efficacy outcome will include analyzing the outcome as observed, that is, whether or not rescue medication was used.

10.3.3.2. Secondary Analyses

The following secondary categorical outcomes will be analyzed in a similar manner as the primary, that is, using the same logistic regression model. Nonresponder imputation will be used for these analyses unless otherwise noted.

- EASI75 at Week 16 and 1 year. EASI75 is defined as having an improvement of at least 75% from baseline. Besides NRI, this outcome will also be analyzed using observed cases, that is, whether rescue medication was given or not.
- EASI90 at Week 16. EASI90 is defined as having an improvement of at least 90% from baseline.
- EASI50 at Week 16. EASI50 is defined as having an improvement of at least 50% from baseline.
- SCORAD75 at Week 16 and 1 year. SCORAD75 is defined as having an improvement of at least 75% from baseline.
- SCORAD90 at Week 16. SCORAD90 is defined as having an improvement of at least 90% from baseline.
- IGA score of 0 or 1 (clear or almost clear skin) and ≥ 2 -point improvement from baseline at Week 4 and 1 year.

- IGA of 0 at 16 weeks.
- 4-point improvement in Itch NRS at 1 week, 2 weeks, 4 weeks, and 16 weeks.

The following continuous measures will be analyzed with the MMRM analysis described above unless otherwise noted. Contrasts within the MMRM analysis will be used to assess treatment differences for time points of interest as specified above in the list of objectives.

- Mean change from baseline in the following outcome measures:
 - ADSS Item 2
 - EASI score
 - SCORAD score
 - BSA
 - Itch NRS
 - Skin Pain NRS
 - POEM
 - PGI-S-AD
 - PROMIS-Depression
 - PROMIS-Anxiety
 - DFI
 - CDLQI and IDQOL total score
 - WPAI-AD-CG
 - EQ-5D-Y
 - PRISM

Baricitinib tablet or oral suspension product acceptability and palatability during the PK lead-in period will be summarized categorically (frequency and percentage) by age group, for each visit separately and in aggregate.

The EASI total score and SCORAD total score will also be analyzed as observed, that is, not assuming missing values after rescue medication is given.

The following categorical data will be analyzed using Fisher exact test described above unless otherwise noted.

- Patients requiring rescue with TCS
- Patients requiring rescue with systemic treatments
- School days missed

The following measures will be analyzed by an ANCOVA with treatment and baseline value in the model.

- Mean number of days without use of TCS over 16 weeks
- Mean gram quantity of TCS used over 16 weeks (tube weights)

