5.1. Overall Design

Study I4V-MC-JAIP (JAIP) is a Phase 3, multicenter, randomized, double-blind, placebo-controlled, parallel-group, outpatient study evaluating the pharmacokinetics, efficacy, and safety of baricitinib compared with placebo in pediatric patients with moderate-to-severe AD. The study is divided into 5 periods, a 5-week Screening period, a 2-week Open-label PK lead-in period, a 16-week Double-Blind Treatment period, an up to 5-year Long-term Extension period, and a 4-week Post-treatment Follow-up period. While the primary objective of this study is to investigate whether baricitinib is superior to placebo in the treatment of the signs and symptoms of AD in pediatric patients, an important secondary objective of the study is to assess the ability of baricitinib to reduce or eliminate the need for use of topical anti-inflammatory agents, the use of which is frequently a concern among parents and caregivers of pediatric AD patients.

Approximately 465 patients 2 to <18 years of age who have responded inadequately to or who are intolerant to topical therapy will be enrolled into the study, of which, approximately 25 patients will be enrolled into the Open-label PK Lead-in period (Study Period 2). The remaining patients (at least 440 patients) will be randomized at a 1:1:1:1 ratio to receive placebo QD, baricitinib low dose QD, baricitinib medium dose QD, or baricitinib high dose QD (110 patients in each treatment group with at least 320 patients 10 to <18 years old and at least 120 patients 2 to <10 years old).

The original protocol was written as a monotherapy study (including TCS washout), and the open-label PK Lead-in period (Study Period 2) will be conducted as such. Protocol amendment JAIP(a) permits the use of background low- and medium-potency TCS, and all patients participating in Study Period 3 (Double-blind treatment) will follow this for subsequent amendments including the amendment, JAIP(b).

Patients will be stratified at randomization according to disease severity (IGA 3 vs. 4) and geographic region (if the planned country allocation justifies). Definitions of geographic regions and plan for analysis by region will be described in the statistical analysis plan (SAP).

Study governance considerations are described in detail in [Appendix 3](#).

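### The 4-point Itch NRS response is tested without adjustment for baseline itch, which gives up some power that data already collected could recover

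*Protocol*

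**What the plan says.** Protocol 10.3.3.1 gives the primary logistic model: region, disease severity (IGA), age, treatment, and treatment-by-age. Section 10.3.3.2 carries it over to the binary secondary endpoints: "The following secondary categorical outcomes will be analyzed in a similar manner as the primary, that is, using the same logistic regression model". The list that follows includes EASI75, EASI90, SCORAD75 and the 4-point Itch NRS response, with nonresponder imputation.

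Section 10.3.1 names as a multiplicity-controlled key secondary the "proportions of patients achieving a 4-point improvement in Itch NRS at 1 week, 2 weeks, 4 weeks, and 16 weeks". Section 4 (Table JAIP.3) limits it to patients aged 10 or over.

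For continuous measures, Itch NRS among them, the MMRM in 10.3.1 includes "baseline score and baseline score-by-visit interaction as fixed continuous effects", and the ANCOVA there includes the baseline value.

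Section 5.1.1 defines the baseline of the daily diary measures as the mean of the 7 days before Visit 2. Section 6.1, criterion 3, sets minimum EASI, IGA and affected body surface area at entry, but no minimum itch.

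**The concern.** Itch NRS runs from 0 to 10 (9.1.4.2), and response is an absolute drop of 4. A patient whose baseline is below 4 cannot respond on any treatment. Above 4, the chance of response may still depend on the starting value. Baseline itch is therefore tied to the outcome partly by construction, and a two-level investigator rating of skin signs is a weak stand-in for a patient-reported itch score.

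The protocol thus treats one score in two ways. Mean change in Itch NRS is adjusted for baseline itch, while the multiplicity-controlled responder version is not, and no reason is given.

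At stake is power. The itch tests use the smaller population and no power is stated for them. Under the graphical procedure, a missed itch test may also stop alpha from passing on, depending on the scheme in the SAP.

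**Working it through.** **Count and sample size.** The endpoints tested per dose are IGA 0/1, EASI75, EASI90, EASI change, SCORAD75, and Itch NRS at Weeks 1, 2, 4 and 16: 1 + 4 + 4 = 9, of which 4 are itch. Section 10.1 plans at least 320 patients aged 10 to <18 and Section 5.1 says patients "will be randomized at a 1:1:1:1 ratio to receive placebo QD" or one of three doses, so 320 / 4 = 80 per arm.

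**The plan's own figure (primary endpoint only).** Section 10.1: "The proposed sample size (N=440) will ensure a >95% power to detect any difference between the baricitinib high dose and placebo treatment groups" or between medium dose and placebo, "assuming a 10% placebo, 25% medium dose, and 30% high dose response rate for the primary endpoint using a chi-squared test". Section 10.1 gives two-sided alpha 0.05 and Section 5.1 gives n = 110 per arm.

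Power = Φ{[Δ√n − 1.96√(2p̄(1−p̄))] / √(p0(1−p0) + p1(1−p1))}

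- High dose: [0.20 × 10.488 − 1.96 × 0.5657] / 0.5477 = 1.805, so 96.4%.
- Medium dose: [0.15 × 10.488 − 1.96 × 0.5374] / 0.5268 = 0.987, so 83.8%.
- At least one of the two (simulated with a shared placebo arm): 98.4%.

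The claim reproduces for the high dose and for either dose, but not for the medium dose alone. That is a separate matter, unaffected by the itch model. The same formula at 80 per arm gives 89.3% and 70.8%, which matches the first two rows of the table below before baseline itch is added.

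**Simulation 1: baseline itch as a predictor of given strength.** All itch inputs are assumed: baseline normal with mean 6.5 and SD 2, clipped to 0–10; 45% with IGA 4 (odds ratio 1.5 against response); three regions; 80 per arm; 3,000 trials per cell. The test is a two-sided 0.05 Wald test of treatment in a logistic model with severity and region, without and then with baseline itch. Age was left out because only patients aged 10 or over contribute. Power in %, without → with:

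| Response, placebo vs active | OR per SD 1.0 | 1.5 | 2.0 | 3.0 |
|---|---|---|---|---|
| 10% vs 30% | 89.4 → 89.1 | 89.9 → 90.3 | 89.8 → 91.0 | 89.6 → 93.8 |
| 10% vs 25% | 71.3 → 71.2 | 70.2 → 71.1 | 70.8 → 73.6 | 70.8 → 76.8 |
| 15% vs 35% | 84.0 → 84.3 | 83.8 → 84.7 | 84.6 → 86.8 | 83.6 → 89.3 |

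If patients below 4 are also made unable to respond (odds ratio 1.5 above that), the gain is 1.3 to 2.4 points with about 10% of patients below 4 (mean 6.5), and 1.9 to 3.3 points with about 23% below 4 (mean 5.5). The Monte Carlo standard error of one power near 70% is √(0.7 × 0.3 / 3000) = 0.8 points. Differences are less noisy because both models see the same trials, but gains under 1 point should be read as about zero.

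**Simulation 2: itch score cut at a 4-point drop.** Week 16 itch = constant + slope × baseline + residual (SD 2.2), so improvement = (1 − slope) × baseline − constant − residual. Baseline matters through 1 − slope and drops out at slope 1. Inputs: 15% vs 30% response, 80 per arm, baseline mean 7, SD 1.8, 2,000 trials. Gain in power points from adding baseline itch:

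| Slope (1 − slope) | No imputation | 15% imputed nonresponders | 25% imputed |
|---|---|---|---|
| 0.3 (0.7) | 5.5 | 5.4 | 4.0 |
| 0.6 (0.4) | 2.2 | 2.0 | 0.6 |
| 0.8 (0.2) | 0.6 | 0.6 | 0.2 |
| 1.0 (0) | 0.7 | 0.6 | 0 |

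Over baseline means 6.5–7.5 and SDs 1.5–2.2, gains without imputation were about 1 to 9 points at slopes 0.3–0.6 and about 0 to 3 at slope 0.8. With 20% imputed as nonresponders they were about 1 to 5 points. No setting showed a material loss.

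**EASI-type responder.** At 110 per arm, 10% vs 25%, severity already in the model, and odds ratios per SD of 1.0, 0.8 and 0.67, the gains were 0.2, 0.3 and 0.9 points.

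**The case against.** The strongest reply is that nothing here is invalid. Treatment is randomised, so the test holds its level without this covariate. Using one model for the primary and secondary responder endpoints is simple and defensible, and 10.3.1 leaves detailed methods to the SAP. The protocol gives no itch mean, SD, slope or response rate, so nothing in it shows baseline itch to be a strong predictor. Nonresponder imputation weakens any link, because rescued or discontinued patients fail whatever their baseline. The simulations also test at the full 0.05, whereas the graphical procedure may allocate less.

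Most of this stands, and it limits the point to efficiency and the size to a range. It does not remove the point. The protocol states the model terms and does not defer them, and the bound at a baseline of 4 follows from the scale and the entry criteria, not from an assumption. If the SAP restricts the endpoint to patients with baseline itch of at least 4, that bound goes, and only the remaining association with baseline matters.

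A reader might go further and infer that the logistic model has no baseline severity adjustment, or that baseline scores go unused. It does contain baseline IGA 3 versus 4, a stratification factor (7.2), and the MMRM uses the baseline scores. A reader might also infer that EASI75, EASI90 and SCORAD75 suffer equally. They are percentage-change responders, the argument about an absolute drop does not apply to them, and the check on an EASI-type endpoint gave about 0 to 1 point.

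**Conclusion.** The point holds for the Itch NRS response as an avoidable loss of efficiency. The expected gain from adjustment is about 0 to 9 points of power over the inputs tried, typically 1 to 5 once nonresponder imputation is included. It is about 0 if baseline itch is not prognostic given severity, or if follow-up itch tracks baseline point for point. The upper end needs a low slope and little imputation, so it should not be quoted as the expected gain.

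These sizes rest on assumed itch rates and distributions and on 80 per arm. Simulation 2 was framed for Week 16; the gain at Weeks 1, 2 and 4 could differ, and would be smaller if early scores stay closer to baseline. The documents do not support reading this as bias, type I error inflation or an error in the power statement, which concerns the primary endpoint only.

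**What to change.** In 10.3.1 and 10.3.3.2, state that the logistic model for the 4-point Itch NRS response at Weeks 1, 2, 4 and 16 also includes baseline Itch NRS (7-day mean before Visit 2) as a continuous covariate, with the existing terms kept. Carry the same wording into the SAP before unblinding, since a covariate added afterwards is open to challenge. Baseline EASI or SCORAD may be added to their own responder models for consistency, with little gain expected.

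The cost is one degree of freedom per model and a change of wording. No new data are needed. The odds ratio becomes conditional on baseline itch and is no longer the same quantity as under the current model; the percentages, their differences and confidence intervals required by 10.3.1 are still reported.
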